2/2/2015

Title: Mucosal impedance in eosinophilic esophagitis and the effect of treatment

Co-Principal Investigator: [name] and [name] MD

Co-Investigators: [REDACTED]

Study Coordinators: [REDACTED]
[REDACTED]

Background:

Eosinophilic esophagitis (EoE) is a chronic disease characterized by esophageal eosinophilia leading to inflammation and fibrosis in response to food antigens. One of the presumptions in this disease is that antigen recognition occurs in the esophagus by dendritic cell recognition and generation of a TH2 allergic response. Although it is speculated that the esophageal epithelium increases its permeability to allow for antigen penetration, this is not well proven.

Mucosal impedance reflects the ability of electric current to flow between two sensors while in contact with the epithelium. An increase in current flow is presumably due to an increase in ions and water crossing the membrane, which are good conductors of electricity. Through this technique an overall measure of “leakiness” of the esophageal epithelium is obtained. This increased permeability may reflect epithelial destruction as in erosive esophagitis, a change in epithelium from squamous to columnar as in Barrett’s esophagus or in conditions in which there are dilated intercellular spaces as has been observed in both gastroesophageal reflux and eosinophilic esophagitis.

While standard diagnostic evaluation for EoE includes upper endoscopy with esophageal biopsies, assessment of mucosal impedance is not. Recently, a new technology has emerged allowing for direct assessment of mucosal impedance at the time of routine upper endoscopy. Yuksel and colleagues have described use of a 2mm diameter single-channel catheter used during the time of EGD which demonstrated lower mucosal impedance in areas of erosive esophagitis and in the mucosa of patients with nonerosive reflux disease compared to healthy controls.¹ In the same manner, mucosal impedance may be lower in patients with EoE, allowing for submucosal antigen exposure and the characteristic Th2 response.

Hypothesis:

Patient with eosinophilic esophagitis have diminished mucosal impedance, reflecting increased permeability to allergens occurring at least in the esophagus and possibly in the buccal mucosa.

Primary Aim:

1. Assess mucosal impedance in patients with EoE of both the esophageal and buccal mucosa.

Secondary Aim:

2. Changes in mucosal impedance in patients with EoE following treatment

Methods:

Study Design:

Patients referred to the Mayo Clinic Rochester either with an establish or suspected diagnosis of EoE will be identified. Those scheduled for clinically indicated upper endoscopy for esophageal biopsies either for initial diagnosis or activity assessment of EoE will be studied. After investigation of established or suspected EoE, a total of 75 patients with confirmed EoE patients. In addition, patients undergoing clinically indicated upper endoscopy for indications either than gastroesophageal reflux or dysphagia will be studied as controls. A total of 10 control patients will be studied.

Inclusion criteria:

- Adults ages 18-90 undergoing clinically indicated upper endoscopy
- Patients with EoE, defined as dysphagia with histologic finding of greater than or equal to 15 eosinophils per high powered field on esophageal biopsy despite at least 6 weeks of twice daily proton pump inhibitor therapy
- Patients undergoing clinically indicated upper endoscopy for indications other than dysphagia or GERD with normal appearing esophageal mucosa.

Exclusion criteria:

- Medical conditions such as severe heart or lung disease that preclude safe performance of endoscopy
- Patients with conditions known to be associated with esophageal eosinophilia, including Crohn's disease, Churg-Strauss, achalasia, and hypereosinophilic syndrome
- Inability to read due to: Blindness, cognitive dysfunction, or English language illiteracy

Study Flow:

Patient undergoing clinically indicated endoscopy and esophageal biopsies for diagnosis or assessing activity of eosinophilic esophagitis will be identified. In addition, patients undergoing

clinically indicated upper endoscopy for indications other than dysphagia or GERD will be identified:

1. Before commencing the procedure, a baseline impedance will be obtained by asking the patient to hold the end of the probe against his/her buccal mucosa for 1 minute for an initial reading.
2. Clinically indicated endoscopic exam will be completed
3. On withdrawal of the upper endoscope into the esophagus, a 2.13mm mucosal impedance catheter (Figure) will be passed through the channel of the standard upper endoscope.
4. The probe will be placed on the esophageal mucosa 5cm above the gastroesophageal junction for 5 seconds and recordings obtained.
5. In patients with suspected or established EoE in whom clinically indicated esophageal biopsies are indicated, 2 biopsies will then be obtained at this level.
6. The scope will then be withdrawn to 10 and 20 cm above the gastroesophageal junction and the same procedure including biopsies performed respectively.
7. In total, six biopsies will be taken which is part of the guideline recommended protocol for eosinophilic esophagitis for clinical purposes.
8. Biopsies in patients undergoing clinically indicated upper endoscopy for indications other than GERD or dysphagia in whom biopsies are not ordered will undergo the same protocol, except esophageal biopsies will not be obtained.

There is minimal risk associated with this study. Upper endoscopy carries an approximate 1 in 3,000 risk of perforation, bleeding, and infection. As this is a clinically indicated study, there is no increased risk from the standpoint of endoscopy for enrolled patients. The impedance catheter measures only 2.13mm in diameter and is flexible with a blunt end. Given the catheter size and the fact that it is passed with direct endoscopic visualization, risk of complications such as perforation or bleeding are minimized and are essentially no different than standard EGD with esophageal biopsies. In fact, in the initial description of use of this catheter 69 patients were studied with no catheter associated complications were reported.¹ In addition, as impedance recording requires on average 5 seconds per level to complete, the protocol will lengthen the procedure time on average 15 seconds which will not have clinically relevant implications regarding need for conscious sedation and procedure related risk. There are no additional risks to the subject adding the buccal mucosal impedance testing.

Impedance testing

Statistical Analysis:

[figure not shown]
As a pilot, ten patients will be studied before and after treatment for eosinophilic esophagitis. This number of patients will be increased if there are treatment failures until there is a total of ten effectively treated patients studied. Effective treatment is defined by the elimination of esophageal eosinophilia on follow up endoscopic biopsy. Ten control patients without esophageal disease will be studied.

Primary Endpoint:

1. Mean and median mucosal impedance in patients with EoE patients compared to controls

Secondary Endpoints:

2. Maximal mucosal impedance in EoE patients compared to minimal mucosal impedance in control patients to determine a potential diagnostic cutoff value
3. Mean and median mucosal impedance in EoE patients post treatment in comparison to pretreatment

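### The unexplained 75:10 split gives the primary EoE-versus-control comparison the precision of about 18 per group; shifting planned slots to controls would sharpen it without a larger study

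*Combined protocol and SAP*

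**What the plan says.** Study Design plans "a total of 75 patients with confirmed EoE patients" and, for the comparison group, "A total of 10 control patients will be studied". Statistical Analysis repeats the second number: "Ten control patients without esophageal disease will be studied".

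The Primary Endpoint is "Mean and median mucosal impedance in patients with EoE patients compared to controls". The first of the Secondary Endpoints is "Maximal mucosal impedance in EoE patients compared to minimal mucosal impedance in control patients to determine a potential diagnostic cutoff value".

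The only other sized objective is the before-and-after pilot in Statistical Analysis, which starts from ten patients: "This number of patients will be increased if there are treatment failures until there is a total of ten effectively treated patients studied".

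The documents give no significance level, power, SD, target difference or rationale for either group size. They state no overall total; 85 is simply 75 + 10.

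**The concern.** The precision of a difference between two groups is governed mainly by the smaller group. Here that group is less than one seventh the size of the other, and it serves both the primary endpoint and the control side of the cutoff endpoint. Once the controls are fixed at ten, further EoE patients add little to the primary comparison. No stated objective calls for 75 EoE patients, and the pilot needs ten effectively treated ones.

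At stake is how large an impedance difference the study can detect or estimate usefully. Too few controls cannot be made good at the analysis stage.

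**Working it through.** The plan has no power or precision figure to reproduce, so the check starts from its counts.

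**Inputs.** From Study Design and Statistical Analysis: 75 EoE patients and 10 controls. Assumed, because not stated: two-sided 5%, 80% power, no dropout, and equal SDs at first (relaxed in step 3). Differences are in SD units.

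**1. Precision at 75:10.**
- SE = √(1/75 + 1/10) = √0.11333 = 0.337 SD.
- Equivalent equal group size = 2 × 75 × 10 / 85 = 17.6 per group.
- Share of the variance due to controls = 0.1 / 0.11333 = 88%.
- Dropping 20 EoE patients with controls still at ten: √(1/55 + 1/10) = 0.344 SD, a rise of 2%.

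**2. Reallocation with the sum kept at 85.** The detectable difference and power come from the noncentral t distribution with n₁ + n₂ − 2 degrees of freedom.

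| EoE:control | SE (SD) | Equivalent per group | Detectable at 80% power (SD) | Change | Power at 0.8 SD |
|---|---|---|---|---|---|
| 75:10 | 0.337 | 17.6 | 0.954 | – | 65% |
| 65:20 | 0.256 | 30.6 | 0.725 | −24% | 87% |
| 55:30 | 0.227 | 38.8 | 0.643 | −33% | 94% |

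The largest possible cut, at 43:42, is 36%, so 55:30 captures most of it. The percentages are the same at 90% power.

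**3. Unequal SDs.** Let r = EoE SD / control SD. Then SE = √(r²/n_EoE + 1/n_control) in control-SD units. Reduction in SE from 75:10:

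| r | 65:20 | 55:30 |
|---|---|---|
| 0.5 | 28% | 39% |
| 1 | 24% | 33% |
| 1.5 | 19% | 24% |
| 2 | 15% | 17% |
| 3 | 7% | 5% |

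Example for r = 2: √(4/75 + 1/10) = 0.392 and √(4/55 + 1/30) = 0.326, a fall of 17%. The gain keeps its direction across this range, but its size depends on r. At r = 3 the smaller shift does slightly better.

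**4. The cutoff endpoint.** Under normality, the expected minimum of 10 controls lies 1.54 SD below their mean; with 30 controls it lies 2.04 SD below. The expected EoE maximum lies 2.40 SD above the EoE mean with 75 patients and 2.29 SD above with 55. With equal SDs, the separation of means at which the expected extremes just stop overlapping is:
- 75:10: 2.40 + 1.54 = 3.94 SD
- 55:30: 2.29 + 2.04 = 4.33 SD

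More controls therefore make the planned maximum/minimum comparison harder to satisfy.

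The result differs if a cutoff is judged by specificity. With all n controls above it, the exact lower 95% limit is 0.025^(1/n): 69% for 10, 83% for 20 and 88% for 30. The sensitivity interval hardly changes: an observed 80% has exact 95% limits of 69–88% with 60/75 and 67–90% with 44/55.

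**5. Room for the pilot.** Ten effectively treated and re-examined patients are 13% of 75 (10/75), 15% of 65 (10/65) and 18% of 55 (10/55).

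**The case against.** **The study may be adequate as it stands.** A reader might infer from the table that the primary comparison is underpowered. The documents do not support that, because they state no target difference or SD. At 75:10 and equal SDs, power is about 84% at 1.0 SD, 94% at 1.2 SD and 99% at 1.5 SD. The calculation also covers means only, while the endpoint names the median too. This objection stands and limits the point to efficiency.

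**The total of 85 is not a cap.** This also stands. EoE patients and controls are found through different clinical indications, and nothing shows that a control displaces an EoE patient. Adding controls while keeping 75 EoE patients would do better still: 0.712 SD at 75:20 and 0.611 SD at 75:30. Holding the sum at 85 shows only that the gain does not require a larger study.

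**The study is a pilot, and the primary aim concerns EoE patients.** The pilot wording is attached to the before-and-after patients, although the ten controls appear in the same paragraph. The Primary Aim does speak of assessing impedance in EoE, but the Primary Endpoint is a comparison with controls. No within-EoE precision target or subgroup is given that would explain 75.

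**More controls do not rescue the cutoff.** It is tempting to read reallocation as curing the cutoff endpoint too. As that endpoint is written it does not, because the control minimum falls as controls are added.

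**Controls may be hard to recruit.** The documents do not address this. Controls are already having an indicated endoscopy, those without ordered biopsies have none taken, and the plan puts the added procedure time at about 15 seconds on average.

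**Conclusion.** The point holds as one of inefficient, unexplained allocation. Under equal SDs, 85 patients split 75:10 inform the primary comparison about as well as 18 per group. At the same sum, 65:20 cuts the detectable difference by 24% and 55:30 by 33%. A cut of about a third therefore needs both equal SDs and roughly 28 or more controls. At 55:30 the SE reduction ranges from 39% to 5% as the EoE/control SD ratio goes from 0.5 to 3.

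Two stronger conclusions do not follow. The trial is not shown to be underpowered, and changing the numbers does not repair the maximum/minimum cutoff comparison. The better lower limit for specificity applies only if that comparison is replaced. The change is worth making because it is cheap and the gain keeps its direction throughout the range examined.

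**What to change.** Amend three numbers: the EoE and control counts in Study Design and the control count in Statistical Analysis. Examples are 65 EoE and 20 controls, or 55 and 30. Give the reason for the split and the assumed SDs. Keep enough EoE patients to reach ten effectively treated pairs, given the expected rates of treatment response and repeat endoscopy. If controls can be added without displacing EoE patients, keeping 75 and raising the controls is also acceptable.

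Separately, replace the maximum/minimum rule in Secondary Endpoints with the sensitivity and specificity of a cutoff, each with a confidence interval. Without this, the added controls do not help that endpoint.

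The cost is a protocol amendment with planned enrolment still at 85. There would be 10 to 20 fewer EoE patients for description within EoE and for the before-and-after pool. Consent effort would rise among controls, whose recruitability is undocumented and should be checked first.

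### The control criterion screens the reason for endoscopy and the look of the mucosa, not reflux itself, although the controls are described as free of esophageal disease

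*Combined protocol and SAP*

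**What the plan says.** All places are in the combined protocol and SAP.

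- **Inclusion criteria (controls):** "Patients undergoing clinically indicated upper endoscopy for indications other than dysphagia or GERD with normal appearing esophageal mucosa". The general age limits also apply.
- **Exclusion criteria:** conditions that make endoscopy unsafe; "Patients with conditions known to be associated with esophageal eosinophilia, including Crohn's disease, Churg-Strauss, achalasia, and hypereosinophilic syndrome"; and inability to read. Reflux is not named.
- **Study Flow:** no step asks about reflux history, symptoms or acid suppression. Controls with no biopsies ordered are not biopsied.
- **Statistical Analysis:** "Ten control patients without esophageal disease will be studied". The section does not say how this is established.
- **Background:** the cited catheter study found lower impedance in erosive esophagitis and "in the mucosa of patients with nonerosive reflux disease compared to healthy controls". The Background also mentions "dilated intercellular spaces as has been observed in both gastroesophageal reflux and eosinophilic esophagitis".
- **Endpoints:** the primary endpoint compares mean and median impedance in EoE with controls. Secondary endpoint 2 sets the EoE maximum against "minimal mucosal impedance in control patients to determine a potential diagnostic cutoff value".

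**The concern.** The two descriptions of a control do not match. One is a set of checks on the endoscopy request and on what the endoscopist sees. The other is a statement about the patient's disease status. Non-erosive reflux falls between them: it leaves no erosions to see, and the indication rule removes it only when it is the reason for the procedure.

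This matters because, on the plan's own account, reflux moves impedance in the direction expected for EoE. Each control with reflux makes the control group look more like the EoE group. Two results are exposed: the esophageal contrast in the primary endpoint, which rests on ten controls, and the control minimum in secondary endpoint 2, which a single patient can set.

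The point concerns esophageal readings only. The Primary Aim is to "Assess mucosal impedance in patients with EoE of both the esophageal and buccal mucosa", but the documents say nothing about reflux and buccal impedance.

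**Working it through.** **1. Text check.** Take a patient with known or symptomatic non-erosive reflux who is scoped for an unrelated reason.

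| Check | Result |
|---|---|
| Age range | passes |
| Indication other than dysphagia or GERD | passes |
| Normal-looking mucosa | passes |
| Safety, eosinophilia-related and reading exclusions | not caught; reflux is not named |
| Any Study Flow step | none asks |
| Statistical Analysis description | does not fit, but no check is attached |

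**2. Inputs for a sense of scale.** From the documents: 75 EoE patients and 10 controls. The documents give no reflux prevalence, reflux shift, SD, test or alpha, so there is no planned figure to reproduce. Assumed here: a share q of 10–20% of controls with reflux; a reflux shift that is a fraction f of the EoE shift, from 0.5 to 1 (1 is the worst case); normal data with SD 1; a pooled t-test at two-sided 0.05.

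**3. Shrinkage of the mean difference.** Observed/true = 1 − q·f.
- q = 0.1: 1 − 0.05 = 0.95 (f = 0.5); 1 − 0.10 = 0.90 (f = 1)
- q = 0.2: 1 − 0.10 = 0.90 (f = 0.5); 1 − 0.20 = 0.80 (f = 1)

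The shrinkage is therefore 5–20%.

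**4. Power.** The standard error is √(1/75 + 1/10) = 0.337 SD, on 83 degrees of freedom. Power with clean controls comes from the noncentral t. The other columns come from simulation, 100,000 studies per cell, with simulation error of about 0.2 percentage points.

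| True difference | Clean | f = 0.5, q = 0.1 | f = 0.5, q = 0.2 | f = 1, q = 0.1 | f = 1, q = 0.2 |
|---|---|---|---|---|---|
| 0.75 SD | 60% | 55% | 50.5% | 51% | 42% |
| 1 SD | 84% | 79% | 75% | 74% | 64% |
| 1.5 SD | 99% | 98.5% | 97% | 96% | 90.5% |
| 2 SD | >99.9% | ≥98% | ≥98% | ≥98% | ≥98% |

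**5. Control minimum.** With clean controls the expected minimum of ten lies 1.54 SD below their mean. Reflux lowers it by 0.07–0.34 SD at a true difference of 1 SD and by 0.19–0.98 SD at 2 SD. At 1 SD the lowest control is a reflux patient in 18–34% of studies (f = 0.5) or 29–50% (f = 1). If reflux had no effect, that figure would be 10–20%.

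For comparison, at 1 SD the EoE maximum exceeds the control minimum by 2.94 SD on average with clean controls, and by 3.01–3.29 SD with reflux present.

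**6. What a screen recovers.** If it catches a share s of reflux patients (assumed), the remaining prevalence is q(1 − s)/(1 − qs).
- s = 0.5: 0.05/0.95 = 5.3%; 0.10/0.90 = 11.1%
- s = 0.8: 0.02/0.92 = 2.2%; 0.04/0.84 = 4.8%

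At s = 0.8, power at 1 SD returns to 83–81% (f = 0.5) or 82–79% (f = 1).

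**7. Reflux on the EoE side.** If a share r of EoE patients also has reflux, and its effect simply adds to that of EoE (assumed), observed/true = 1 + f(r − q). Equal shares cancel. With q = 0 and r = 10–20%, the ratio is 1.05–1.20. Screening only controls can therefore turn shrinkage into inflation of similar size.

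**The case against.** The strongest reply is that the Statistical Analysis wording is itself a requirement, which a patient with known reflux would fail. The indication rule is also repeated in several places and keeps out patients scoped because of reflux. That reading is tenable, and it narrows the gap to the absence of any stated check. It does not close the gap, because staff who enrol from the listed criteria would admit the patient. The eosinophilia exclusion is worded as an open list, but stretching it to reflux would be left to each investigator.

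Two further objections stand:

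- **The size is assumed.** The shift rests on one Background sentence with no effect size, and the full-shift case is a worst case. At half shift and 10% prevalence, power at 1 SD drops only from 84% to 79%. Below 1 SD the losses persist, but power there is already inadequate with clean controls, so having only ten controls is the main constraint.
- **Screening only controls is asymmetric.** No criterion keeps reflux out of the EoE group. The EoE definition requires eosinophilia "despite at least 6 weeks of twice daily proton pump inhibitor therapy", which does not rule out coexisting reflux. If reflux is removed from controls alone, reflux in EoE patients could inflate the difference. The existing indication rule already does this in part. The fix has to deal with it.

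A reader might infer that the gap could produce a spurious finding of low impedance in EoE. It could not: if reflux lowers impedance, as the Background reports, its presence in controls works against that finding. A reader might also infer that cleaner controls would rescue the cutoff. At 1 SD the extremes already overlap by 2.94 SD with clean controls, so the use of extremes is a separate and larger weakness there.

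**Conclusion.** The point holds as a mismatch between the control criterion and the description of controls in the Statistical Analysis section. Its effect is a bias of the esophageal EoE-control difference toward zero and a lower control minimum.

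The actual size is unknown. Under the assumptions stated, the primary contrast loses 5–20%. The power cost is material at true differences of about 1 SD or less and small from 1.5 SD upward. These figures depend on the assumed prevalence, shift, SD, alpha and test.

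The documents do not support saying that reflux patients will be enrolled in any particular number, that the study is invalid, or that the buccal comparison is affected. This is a worthwhile, inexpensive improvement, best made before controls are measured.

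**What to change.** 1. **Control criterion.** Add to the Inclusion criteria that patients with a known GERD diagnosis, current heartburn or regurgitation, or treatment for reflux are not eligible as controls. Check this by chart review and a short symptom question. State that silent reflux is not detected. No control biopsies are needed.
2. **Both groups.** Record the same reflux history and symptoms, and PPI use at the index endoscopy, in EoE patients and controls, and report them by group.
3. **Sensitivity comparison.** Repeat the esophageal EoE-control comparison without EoE patients who have known coexisting reflux.

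**Cost.** One eligibility line, a symptom question, a few data fields and one extra analysis. Candidates needed for ten controls are 10/(1 − qs). At s = 0.8 that is 10/0.92 = 10.9 to 10/0.84 = 11.9, so about 11–12. If 25–40% of candidates are turned away because heartburn without reflux also counts (assumed), it is 10/0.75 = 13.3 to 10/0.60 = 16.7, so about 13–17.

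**Downsides.** Recruitment of controls is slightly slower and silent reflux stays in. Removing treated patients may widen a PPI imbalance between groups. The documents establish neither the size nor the direction of a PPI effect, nor that EoE patients are taking a PPI when measured. A cutoff from cleaner controls may look better than it would in ordinary endoscopy patients. The use of the EoE maximum and control minimum for the cutoff needs its own remedy.

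### Only controls must have normal-appearing mucosa, so coexisting erosive or Barrett's mucosa can lower esophageal impedance in the EoE group alone; the size is unknown and the remedy is cheap

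*Combined protocol and SAP*

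**What the plan says.** The inclusion criteria treat the two groups differently. Controls are "Patients undergoing clinically indicated upper endoscopy for indications other than dysphagia or GERD with normal appearing esophageal mucosa". The EoE group is "Patients with EoE, defined as dysphagia with histologic finding of greater than or equal to 15 eosinophils per high powered field on esophageal biopsy", found "despite at least 6 weeks of twice daily proton pump inhibitor therapy"; nothing is required of how the mucosa looks.

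The exclusion criteria cover conditions that make endoscopy unsafe, inability to read, and "Patients with conditions known to be associated with esophageal eosinophilia, including Crohn's disease, Churg-Strauss, achalasia, and hypereosinophilic syndrome". GERD, erosive esophagitis and Barrett's esophagus are not named.

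The Background describes what impedance responds to besides EoE: "This increased permeability may reflect epithelial destruction as in erosive esophagitis, a change in epithelium from squamous to columnar as in Barrett’s esophagus". It adds that an earlier study with an endoscopic impedance catheter "demonstrated lower mucosal impedance in areas of erosive esophagitis and in the mucosa of patients with nonerosive reflux disease compared to healthy controls".

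Under Study Flow, step 4 fixes the lowest site: "The probe will be placed on the esophageal mucosa 5cm above the gastroesophageal junction for 5 seconds and recordings obtained". Step 6 repeats the measurement at 10 and 20 cm. The primary endpoint, under Statistical Analysis, compares mean and median impedance between EoE patients and controls. No adjustment or sensitivity analysis is given.

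**The concern.** The hypothesis attributes low impedance to EoE. A patient with dysphagia, a qualifying eosinophil count after the PPI course, and erosions or columnar mucosa reaching 5 cm meets every listed criterion. That patient's reading enters the EoE mean, while a control with the same mucosa would not be eligible. Visible causes of low impedance other than EoE can therefore occur in one group only, and they push the comparison in the direction the study hopes to find.

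The before/after endpoint is open to a related problem. An erosion present at the first endoscopy and healed by the second would be counted as a change due to EoE treatment.

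**Working it through.** **Do the documents close the gap?**

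- *Inclusion:* normal appearance is required of controls only.
- *Exclusion:* the word "including" leaves the list open, but its test is association with esophageal eosinophilia. The documents do not place erosive esophagitis or Barrett's under that heading.
- *PPI course:* this makes erosions less likely. Healing need not be confirmed, the requirement attaches to the qualifying biopsy rather than to the endoscopy at which impedance is read, and it does not address Barrett's.
- *Measurement:* no rule says to avoid, record or drop readings on eroded or columnar mucosa.
- *Analysis:* no adjustment, stratification or sensitivity analysis is given.

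The gap is open. The support is direct for erosive esophagitis, where lower impedance is reported. For Barrett's it is by mechanism only, through increased permeability.

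**How large could the effect be?** The plan gives no SD, effect size, power or lesion prevalence, so there is no figure to reproduce. What follows is an illustration.

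Inputs from the protocol: 75 EoE patients and 10 controls. Assumed: a fraction f = 5-20% of EoE patients has such mucosa at the 5 cm contact point; each such reading is lowered by d = 1-3 SD; readings are normal with a common SD apart from the lesions; EoE itself has no effect.

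1. Standard error of the mean difference at one level, without lesions: √(1/75 + 1/10) = √0.1133 = 0.337 SD.
2. Shift in the 5 cm mean: f × d, from 0.05 × 1 = 0.05 SD to 0.20 × 3 = 0.60 SD.
3. The lesions also widen the EoE distribution, to variance 1 + f(1−f)d². At f = 0.20 and d = 3 this is 1 + 0.16 × 9 = 2.44, so the standard error is √(2.44/75 + 1/10) = 0.364 SD. The worst case is then 0.60/0.364 = 1.65 standard errors; ignoring the added variance it would be 0.60/0.337 = 1.8. The mildest case is 0.05/0.337 = 0.15.
4. Shift in the 5 cm median: solve (1−f)Φ(m) + fΦ(m+d) = 0.5 for m. This gives m = −0.044 at f = 0.05, d = 1, and m = −0.316 at f = 0.20, d = 3. The range is about 0.04-0.32 SD.
5. Shift in a mean over three levels with only 5 cm affected: f × d/3, from 0.05/3 = 0.017 to 0.60/3 = 0.20 SD. These are single-level SD units. The average's own standard error equals the single-level one only if the levels are perfectly correlated, and is smaller otherwise.

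**Cost in precision of dropping readings.** Controls contribute 0.1/0.1133 = 88% of the variance. Losing 10 of the 75 EoE readings at a level gives √(1/65 + 1/10) = 0.340 SD, against 0.337 SD.

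**The case against.** The strongest reply is that the size rests wholly on assumption. What counts is not how many EoE patients have any reflux lesion, but how many have eroded or columnar mucosa exactly where the probe touches, 5 cm above the junction, after a qualifying biopsy taken on twice-daily PPI. Nothing in the documents supports a share as high as 20% or a drop as large as 3 SD, and the largest figure needs both together. The 5 cm reading is not itself a named endpoint, the primary endpoint includes a median that roughly halves the worst case, and averaging levels dilutes the shift. All of this stands and limits the claim.

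A reader might infer that the primary comparison is invalid, or that an observed difference would be mostly lesion artefact. The documents do not support that. They give no lesion frequency, and most of the assumed range lies below one standard error. Nor do they show that the buccal comparison is affected. The cutoff endpoint takes the EoE maximum, which a few low readings hardly move.

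The before/after effect is also limited. It needs erosions at a measured site that heal between visits, among about ten effectively treated patients, and it cannot be quantified. Columnar mucosa that persists would largely cancel within a pair.

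A last objection concerns the remedy. An endoscopist who knows the patient's group could remove low readings selectively, and dropping a patient answers a different question from dropping a level. That is a fair reason to choose one rule and apply it before the reading is seen. It is not a reason to leave the gap.

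**Conclusion.** The concern holds in a limited form. The plan as written allows coexisting erosive or Barrett's mucosa to contribute to the EoE-control difference in esophageal impedance, mainly at 5 cm and in the direction of the hypothesis. The PPI requirement reduces this route without closing it.

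The bias could be negligible, or at the joint extreme of the assumed ranges it could exceed one standard error of the 5 cm mean. The documents cannot say which. No figure in the plan is wrong. This is a cheap improvement to the design, not a defect that undermines the study.

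**What to change.** At each endoscopy, in both groups, record from the endoscopic view whether erosions or columnar mucosa are present at each measured level, before the probe is read. The endoscopic examination is already completed before the catheter is passed (Study Flow, steps 2-3), so no extra procedure is needed.

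Prespecify one rule: readings at affected levels are omitted from the esophageal impedance endpoints. EoE-type findings do not trigger it. For the before/after comparison, a level affected at either endoscopy is omitted from both readings of the pair. Report the analysis with all readings alongside. Because the plan does not say how the levels are combined, it should also state how a patient with a missing level is handled; comparing level by level is the simplest way.

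The cost is one recording item per level, a few lost 5 cm readings with almost no loss of precision, and some endoscopist judgement in separating erosions from EoE-type findings. Recording before the reading, together with the all-readings analysis, keeps that judgement visible.
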